4.4 Exclusion criteria

- Known asthma.
- Male < 40 years.
- Female < 40 years, if non-menopausal (had menstruation within the last 12 months) conditioned by a negative urine HCG test
- Severe mental illness which considerably complicates co-operation.
- Language problems that considerably complicate co-operation.
- Current treatment with systemic corticosteroids corresponding to > 5 mg prednisolone per day.
- Systemic antibiotic treatment (if to participate in microbiota sub-study) or systemic corticosteroid treatment within 14 days (also prophylactic Azithromycin).
- Contra-indication to treat with Azithromycin (as listed by the producer).
- Non-bacterial* exacerbation per investigator judgement in the last 3 months.

* Non-bacterial exacerbation per investigator judgement may be guided by

Exacerbation with blood eosinophil $> 0.3 \times 10^9$ cells

Exacerbation with CRP < 100 mg/L

Exacerbation with chest x-ray without sign of pneumonia

4.5 Examinations

The following clinical tests will be performed during the project cf. figure 2.

	Enrollment	Inclusion (Baseline)	After 3 months	After 6 months	After 9 months	After 12 months
Informed consent	X					
Eligibility screening	X					
Blood sample		X	X	X	X	X
Tracheal aspirate and nasal swab		X				X
Lung function measurement (Spirometry)		X				X
Weight		X				X
Height		X				
COPD Assessment Test (CAT)		X				X
MRC-dyspnoea scale		X	X	X	X	X

Figure 2: An overview of examinations that each participant will undergo. The blood test can be performed either at the participant's home or at the outpatient clinic, with intervals of 3, 6, and 9 months.

Blood tests: Electrolyte parameters (sodium, potassium, albumin, creatinine, hemoglobin), liver parameters (conjugated bilirubin, ALT, alkaline phosphatase, INR, LDH), infection parameters (CRP, white blood cell differential count, thrombocytes), D-dimer and HbA1c.

Patients with COPD enrolled in the COPERNICOS clinical trial exhibit physical frailty due to the severity of their illness. Therefore, attendance at one of the trial sites in general is both demanding and stressful for the participants. To reduce the stress and to ease the access for the COPD patients to participate in the trial, the blood tests after 3, 6 9 and 12 months can be performed in the participants' home. Otherwise, they will be performed at one of the local trial sites. It's important to highlight that the full 12-month follow-up, including spirometry, will be conducted in patients' homes if they are unable to visit the trial sites. If the blood test is performed at the participants' home, it will be performed by trial staff either a doctor, a nurse, or a medical student. All staff will be trained in accordance with the current ICH-GCP guidelines. However, the investigator has the ultimate responsibility for all trial related medical decisions. The blood tests will be analyzed by the already approved laboratories for the trial. We aim to ensure that participants, needing the blood test to be taken at home more than one time, will be visited by the same trial staff to contribute to continuity for the patients. The blood tests will only be performed by doctors, nurses or medical student, who will follow all applicable and relevant guidelines and our standard operating procedures (SOP) on handling and storage of blood tests set by the Capital Region of Denmark ("Region Hovedstaden").

Questionnaires: Standardized questionnaires are used. CAT and MRC dyspnea scale are short and simple tests that provide an understanding of the severity and impact of COPD on the participant's daily life.

4.6 Data Collection

Data processing, statistical analysis and publication of the data material will be performed by a PhD student (coordinating investigator) together with health professionals (primary and secondary investigators) from the participating pulmonary medical outpatient clinics. The randomized trial started with the inclusion of participants 05JUL2021, and the last participant is expected to be

included by 31AUG2025. Data collection ceases 31AUG2026, and the project is scheduled to run until 31AUG2026.

A nurse will be responsible for collecting baseline data, performing lung function measurement, weight and height at baseline and the 12-month follow-up as well as performing blood sampling and questionnaires at three-, six- and nine-month follow-ups, according to Fig. 2. Data will be obtained via the electronic health record. Medical decisions are made by doctors only. Proper handling, storage, and delivery of medication and the primary daily project management is handled by the coordinating investigator. Recruitment, medical examinations, and distribution and accounting of medication will be assisted by primary investigators at each centre.

The data collected will be treated confidentially and only by personnel associated with the project. This includes demographic data, health status, current illnesses, medications, medicinal side effects, hospital admissions, and results from various examinations during the trial. Data will be reported in Electronic Case Report Forms (eCRF) specific for each participant. The data is encrypted, stored in online servers and protected by the Data Protection Authority through various security precautions. The physical copies of the CRF are kept in locked archives on the involved departments for 5 years.

Data in eCRF will be handled by the investigator at each centre and in accordance with the Law for Data Protection and the Danish Law for Privacy Regulation.

4.7 Replacement of Azithromycin/Placebo IMP

In the trial, the investigational medicinal product (IMP) consisting of Azithromycin/Placebo will be distributed to the participants. Some participants will receive Azithromycin/Placebo IMP with an

expiry date before the end of the 12-month study period. The data for all distributed Azithromycin/Placebo IMP, including expiry dates, are closely monitored.

Replacement will be coordinated as the expiry date of the Azithromycin/Placebo IMP approaches. In such instances, a designated member of the study team (comprising the investigator, sub-investigator, study nurse, or medical student, all operating under the investigator's supervision and responsibility) will schedule appointments with each participant whose Azithromycin/Placebo IMP is nearing expiration. These appointments will be arranged at a time when the participant is available at home for the replacement of Azithromycin/Placebo IMP. The Azithromycin/Placebo IMP will be transported by the vendor or a courier, both holding all applicable licenses and authorizations for carrying out transportation of medicine, to the participant's home. The medicine will be placed in a package that explicitly states not to open it without prior contact with a member of the study team. The medicine in the package will be delivered to the participant's home. After delivery of the new IMP to the participant's home a notice will be send to the research coordination center at Gentofte Hospital. The vendor or the courier will take the expiring IMP back to the research coordination center at Gentofte Hospital. Thereafter a member of the study team will visit the participant in the participant's home or, if deemed sufficient and safe, perform a phone call. The member of the study team will hereby give a complete instruction for the patient on how to open the new IMP package and ensure correct use of it. Furthermore, the study member will answer all questions that the participants might have. If any medical related issues or problems might appear at any time, the study member will contact the investigator. However, the new Azithromycin/Placebo IMP is almost identical to the expiring one both in look and in content. The Azithromycin/Placebo IMP does not require any specific temperature or storage measures; therefore, it will not be temperature surveilled during the transportation.

All participants in the trial will at time of inclusion get dispensed Azithromycin/Placebo IMP at the site. However, only in cases where Azithromycin/Placebo IMP is set to expiry, the above-mentioned procedure for replacement of Azithromycin/Placebo IMP will be carried out.

The replacement of the Azithromycin/Placebo IMP will be conducted directly at the participant's residence. A designated member of the study team will collect the soon-to-expire Azithromycin/Placebo IMP and document the exchange. Thereafter, the member of the study team will hand over Azithromycin/Placebo IMP with longer expiry date to the participating patient. Detailed list of the newly handed out Azithromycin/Placebo IMP will be made in accordance with the current applicable requirements including but not limited to expiry date, batch number, number of capsules, name and signature of the member of the study team handing over the new Azithromycin/Placebo IMP, study ID etc. After the replacement of the Azithromycin/Placebo IMP, the replaced Azithromycin/Placebo IMP with soon expiry date will be transported back to the research coordination center at Gentofte Hospital. The sponsor has the overall responsibility of the Azithromycin/Placebo IMP but due to the regulations in section 23(2) of the GDP Executive Order only the investigator can carry out IMP deliveries, and in this case IMP replacement. The replacement will be performed in accordance with all current data regulations.

4.8 Research Biobank

The purpose of establishing a research biobank is to investigate the frequency of ICS-induced side effects and the changes in respiratory microbiota in different treatment groups. This biobank will clarify the hypotheses and provide biological materials for future research (Providing that future

projects can obtain a separate approval from the Danish National Committee on Health Research Ethics).

The research biobank will store blood samples, tracheal aspirate samples, and nasal swabs. Tracheal aspirate and nasal swab samples are taken from 40 participants from each treatment arm, in total 160 participants. Approximately 1-5 ml of tracheal aspirate will be collected from each participant. Blood samples are taken from each participant at inclusion and at follow-up every 3 months during the 12-month study period. Approximately 210 ml of blood will be collected during the entire study period corresponding to a maximum of 36 ml per blood draw. All samples are stored in a freezer at -80 degrees Celsius. The freezers are kept in a locked room at each of the participating pulmonary medicine departments.

All samples are pseudonymized and kept for 15 years in accordance with present legislation and data protection laws. Establishment of this research biobank ends **31AUG2027**. Following the end of this study and the research biobank, all surplus biological material will be transferred to a future-research biobank. These samples will also be pseudonymized and kept for 15 years. Permission to store biological material from participants in the research biobank and future-research biobank is a part of the informed consent to participation in the project.

5. Statistical Considerations (Power Calculation)

Participants will be randomized using stratified block randomization (REDCap) to ensure equal distribution of participants at the site, age (less than 70 years vs 70 years or more) and number of hospital-requiring exacerbations within the past 12 months (0-1 vs 2 or more).

The trial will have a target of 444 participants, , included in the project within 48 months, and 111 participants will be allocated to each of the four groups to be examined.

Two sample size calculations have been conducted, one for ICS and one for azithromycin, as there are two interventions being tested (factorial design):

A non-inferiority (1-sided) test for ICS.

Type 1 error limit (α) 2.5%, Power ($1-\beta$) of 80%. ($\alpha = 0.025$, $\beta = 0.2$)

Control group exacerbation/death: 0.3 (30%)

Expected maximum worsening >11% absolute (up to 0.41)

Sample size 444 (222 x 2)

A 1-sided superiority test for azithromycin.

Type 1 error limit (α) 2.5%, Power ($1-\beta$) of 80%. ($\alpha = 0.025$, $\beta = 0.2$)

Control group exacerbation/death: 0.3 (30%)

Expected effect: >10% absolute (up to 0.2)

Sample size 444 (222 x 2)

These two interventions will be published separately in two primary publications, but there will be adjustments in the main analysis to account for whether they received the other intervention. These two analysis teams (separate) will be blinded to an effect estimate of the other intervention.

40 participants from each group will participate in the microbiota sub-study.

Scheduled analyses of data (Interim analysis) will be assessed when half of the participants are recruited. These assessments will be made by the independent Data and Safety Monitoring Board (DSMB) on the two primary endpoints, and for the secondary endpoint “Death or “uncontrolled AECOPD tendency” within 365 days”. Data on primary and secondary power targets will be used for this purpose. DSMB will review the protocol, monitor the guideline, evaluate the trial concerning the recruitment of participants, participants' risk and, based on interim analyses, make recommendations to the investigators on whether to continue or cease the study. DSMB may at any time require an extraordinary interim analysis

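### With 222 per side at one-sided 2.5%, power is about 72% for ICS non-inferiority and 68% for azithromycin, not the stated 80%

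*Protocol*

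**What the plan says.** Protocol Section 5, Statistical Considerations (Power Calculation), describes a factorial trial in which "111 participants will be allocated to each of the four groups to be examined". Each intervention is therefore compared as 222 against 222. Two calculations are given:

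- **ICS:** "A non-inferiority (1-sided) test for ICS", control risk of exacerbation or death 30%, "Expected maximum worsening >11% absolute (up to 0.41").
- **Azithromycin:** "A 1-sided superiority test for azithromycin", control risk 30%, "Expected effect: >10% absolute (up to 0.2").

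Both state "Type 1 error limit (α) 2.5" per cent and 80% power, with alpha repeated as 0.025 and beta as 0.2. Both end with "Sample size 444 (222 x 2"). Section 5.1 names a chi-squared test for the primary endpoint. Section 5 gives no dropout allowance and no assumed true difference for the non-inferiority comparison.

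**The concern.** The two calculations have different targets (an 11-point margin with presumably no true difference, and a 10-point true difference) but give exactly the same sample size. Both totals look small for a one-sided 2.5% test at these risks.

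These are the trial's two primary comparisons, and each is to have its own main publication. If the power statement is wrong, the chance of missing a true azithromycin benefit, or of failing to show non-inferiority when the guided strategy is truly equivalent, is higher than the sponsor, the DSMB and readers have been told. A null azithromycin result or a failed non-inferiority result would then be given more weight than the design supports.

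**Working it through.** **Inputs, all from Section 5:** one-sided alpha 0.025 (z = 1.960); power 0.80 (z = 0.842); control risk 0.30; margin 0.11; azithromycin risk 0.20; 222 per side. The true difference for ICS is not stated and is taken as zero.

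**Trying to reproduce 222 for ICS.** With both sides at 0.30, the variance sum is 2 × 0.3 × 0.7 = 0.42.

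- n per side = (1.960 + 0.842)² × 0.42 / 0.11² = 272.4, so 273 per side and 546 in total.
- Power at 222: the standard error is √(0.42/222) = 0.0435, and Φ(0.11/0.0435 − 1.960) = Φ(0.569) = 71.5%. Exact binomial enumeration gives 71.6%.
- If the entry is read instead as detecting 0.30 against 0.41, 592 in total are needed and power at 222 is 67.9%.

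**Trying to reproduce 222 for azithromycin.** The variance sum is 0.3 × 0.7 + 0.2 × 0.8 = 0.37.

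- Unpooled: n per side = (1.960 + 0.842)² × 0.37 / 0.10² = 290.4, so 291 per side and 582 in total.
- Pooled (mean risk 0.25): n per side = (1.960 × √0.375 + 0.842 × √0.37)² / 0.10² = 293.2, so 294 per side and 588 in total. A continuity correction raises this to 313 per side.
- Power at 222: unpooled, Φ(0.10/√(0.37/222) − 1.960) = 68.8%; pooled, 68.3%; exact enumeration of the chi-squared test, 68.5%.

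**Shortfall against 444:** 546 − 444 = 102 participants for ICS, and 582 − 444 = 138 to 588 − 444 = 144 for azithromycin. This is too large to be rounding.

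**Which inputs come close to 222?** A one-sided alpha of 0.05 (z = 1.645).

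| Comparison | n per side at 0.025 | Power at 222, alpha 0.025 | n per side at 0.05 | Power at 222, alpha 0.05 |
|---|---|---|---|---|
| ICS, margin 0.11 | 273 | 71.5% | 215 | 81.2% |
| Azithromycin, 0.30 v 0.20 | 291–294 | 68.3–68.8% | 229–231 | 78.6–78.9% |

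At one-sided 5%, power is within 2 points of 80% for both, although neither calculation returns exactly 222. That 5% was entered while 2.5% was written is an inference, not something the protocol shows.

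**What 222 per side supports at 80% power and one-sided 2.5%:**

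- ICS: margin = 2.802 × √(0.42/222) = 0.122, or 12.2 points.
- Azithromycin: a fall from 30% to about 18.6%, or 11.4 points.

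**Sensitivity, resting on assumptions not in the protocol:**

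- If 30% is the risk without azithromycin and azithromycin works as planned, each side of the ICS comparison averages (30% + 20%)/2 = 25%. The variance sum becomes 2 × 0.25 × 0.75 = 0.375. The need is then 243.3, so 244 per side, and power at 222 is 76%. Using the within-stratum variance sum of 0.37, to reflect the planned adjustment for the other intervention, gives about 77%.
- With 5% to 10% loss (about 211 to 200 per side), power is 69% to 67% for ICS and 66% to 64% for azithromycin (pooled).

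**The case against.** The arithmetic itself is not in dispute, but several limits deserve weight.

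- **The ICS figure is conditional.** It assumes a true difference of exactly zero. If guided ICS were truly 1 point better (29% against 30%), power would be 79%. This stands as a caveat. However, the primary ICS hypothesis in Section 3 is no apparent loss of efficacy, zero difference is the usual planning assumption for non-inferiority, and no benefit is claimed anywhere. The azithromycin shortfall does not depend on it.
- **ICS power may be nearer 76% to 77%** if azithromycin works and lowers the average risk. That is fair, but it depends on reading the 30% as an azithromycin-free risk, and it still falls short of 80%.
- **The loss figures are illustrative.** Data come through electronic health records (Section 4.6), so loss on admissions and death may be small. The main result uses no loss.
- **The alpha is already stated consistently as 0.025.** This is true within the protocol, so asking for one alpha is a confirmation and does not correct a contradiction.
- **Misstated power does not bias estimates or inflate the type I error**, and the confidence interval will show the precision reached. This is correct and limits the harm to planning and interpretation. The printed power of both primary comparisons is still wrong.

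A separate statistical analysis plan could not resolve this, because no analysis detail makes the protocol's printed inputs yield its printed sample size.

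**Conclusion.** The concern holds: the power statement is wrong as written for both primary comparisons. At the stated one-sided 2.5% with 222 per side, azithromycin has 68.3% to 68.8% power for 30% against 20%. This rests only on figures in the protocol. ICS non-inferiority has 71.5% power for an 11-point margin, given a 30% risk and no true difference, and about 76% to 77% if azithromycin lowers the average risk to 25%. In the base case the type II errors are 28.5% and 31.2% to 31.7%, about 1.4 and 1.6 times the stated 20%. The larger requirement, 582 to 588 participants before any loss, would govern a trial that truly had 80% power for both. Confidence is high, because pooled, unpooled, arcsine, continuity-corrected and exact calculations all point the same way.

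**What to change.** Keep 444 participants and the 11-point margin, and correct Section 5:

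1. State that at one-sided 2.5% with 222 per side, power is about 72% for ICS non-inferiority (30% risk on both sides, no true difference, margin 11 points) and about 68% for azithromycin (30% against 20%).
2. Add that 80% power for azithromycin corresponds to a fall from 30% to about 18.6%.
3. Write down the true difference assumed for ICS. If the 76% to 77% figure is also shown, give the 25% average risk as its assumption.
4. Confirm that one-sided 2.5% is the level for both planning and analysis, and carry it unchanged into the statistical analysis plan. Do not move to 5% to match the sample size.
5. Do not widen the margin to 12.2 points to recover 80%.

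The cost is protocol wording and a less favourable stated power. No further patients are asked for: Section 4.6 expects the last inclusion by 31 August 2025, and reaching 80% for both comparisons would take 138 to 144 more than the target.

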5.1 Primary Endpoints

ICS and Azithromycin

The primary outcome targets admissions and death within 365 days of randomization. This is assessed in the following analysis:

- Number of hospitalization-requiring COPD exacerbations and/or death within 365 days (continuous data: analysis with chi squared test)

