5.3 Data analysis

The four treatment groups will be compared in terms of endpoints at inclusion and follow-up visits every 3 months from trial inclusion with standard statistical tests such as t-test (Dichotomous outcomes), chi-squared test, Fisher's exact test, and time-to-event analyses.

Recurrence of AECOPD, the period between index AECOPD and the next AECOPD, and number of admission-requiring NIV treatment within 365 days are analyzed using Fisher's exact test or Chi-

squared test. Time to AECOPD within 365 days and number of hospitalization-requiring exacerbations within 365 days will be analyzed with t-test and Cox proportional-hazards regression model (unadjusted and adjusted). Mortality rate within 365 days will be analyzed with Chi-squared test or Fisher's exact test (unadjusted) and with Cox proportional-hazards regression model (adjusted).

New onset of diabetes during the study period or occurrence of antibiotic-requiring infections within 365 days will be analyzed using Fisher's exact test or Chi-squared test. Changes in lung function, health-related quality-of-life (CAT), and level of dyspnea (MRC) will be analyzed using analysis of variance (ANOVA). The cumulative ICS dose will be analyzed as mean total cumulative dose from recruitment to end of the study period using t-test, Wilcoxon signed-rank test or Mann-Whitney U test.

6. Risks and Side Effects

Possible side effects from the use of ICS (Beclometasondipropionat) according to pro.medicin.dk are:

Common (1-10%): Pharyngitis, Coughing, Hoarseness, Headache, Candidiasis.

Uncommon (0.1-1%): Blurry vision, Dizziness, Tremor.

Rare (0.01-0.1%): Allergic reactions, Angioedema, Bronchospasm.

Very rare (<0.01%): Adrenal insufficiency. Eosinophilic pneumonia. Erythema, purpura. Decrease in bone mineral density. Glaucoma, cataract. Growth retardation.

Unknown prevalence: Disturbed behavior, Aggressiveness, Anxiety, Depression, Hallucinations, Hyperactivity, Hypercorticism.

Possible side effects from the use of Azithromycin according to pro.medicin.dk are:

Very common (>10%): Abdominal pain, diarrhea, flatulence, nausea.

Common (1-10%): Tiredness or weakness. Decreased appetite. Vomiting, taste perversion. Decreased lymphocyte count. Decreased serum bicarbonate. Arthralgia. Headaches, Paresthesia, Dizziness. Skin itching, rash. Visual disturbances.

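### The plain chi-squared test named for the primary endpoint does not carry the promised adjustment for the other intervention and ignores the randomisation strata, at a modest cost in precision if those strata are prognostic

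*Protocol*

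**What the plan says.** - Section 5 (Statistical Considerations) plans one primary publication per intervention and states that "there will be adjustments in the main analysis to account for whether they received the other intervention". Each comparison is sized at the factorial margin, 222 against 222, from four arms of 111.
- Section 5.1 defines the primary outcome as "Number of hospitalization-requiring COPD exacerbations and/or death within 365 days" and gives its analysis as "continuous data: analysis with chi squared test". It names no stratum, covariate or interval.
- Section 5 also fixes the allocation method: "Participants will be randomized using stratified block randomization (REDCap) to ensure equal distribution of participants at the site, age" (under 70 against 70 or older) and prior hospital-requiring exacerbations (0–1 against 2 or more). No section says that these factors enter the primary analysis.
- Section 5.3 (Data analysis) opens with "The four treatment groups will be compared in terms of endpoints at inclusion and follow-up visits every 3 months". It later lists adjusted Cox models for time to exacerbation, number of hospitalised exacerbations and mortality. It names no covariates and does not assign these models to the primary composite.

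**The concern.** Sections 5 and 5.1 cannot both be followed as written. A chi-squared test on a two-by-two table has no place for a second factor, so either the promised adjustment or the named test must give way. If that choice is made after the data are seen, it is open to the results.

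The strata matter as well. Stratified randomisation balances the arms on the stratifying factors, so the treatment difference varies less from trial to trial than an unadjusted standard error assumes, provided those factors predict outcome. An analysis that ignores them then uses too large a standard error and gives up precision. Both primary comparisons are already below their stated power. Prior hospital-requiring exacerbations are a plausible predictor of an endpoint made up of such exacerbations and death, but the protocol gives no figure for how strong a predictor they are.

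**Working it through.** **The plan's own figure.** Inputs from section 5: control risk 0.30, non-inferiority margin 0.11, azithromycin effect 0.30 to 0.20, one-sided α 0.025, power 80%, 222 per side. The composite is treated as yes/no per participant, as the sample size treats it.

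- ICS: n = 2 × 0.21 × (1.960 + 0.842)² / 0.11² = 272.4, so 273 per side (546 in total).
- Azithromycin, pooled variance under the null: 293.2, so 294 per side (588 in total).
- The stated 222 per side is not reproduced. At 222, power is about 71.5% for ICS and 68.3% for azithromycin.

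**Adjusting for the other intervention only.** In a balanced factorial, a 10-point effect of the other treatment explains 0.25 × 0.10² / (0.25 × 0.75) = 1.3% of outcome variance. A simulation of the trial (444 participants, six sites, assumed permuted blocks of 4) showed azithromycin power changing by 0 to 0.4 points.

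**Adding the strata (ICS comparison).** The protocol gives no risks by stratum. Assume that 25% of participants fall in the group with 2 or more prior admissions, with event risk r, and that overall risk stays at 0.30. The others then have risk q = (0.30 − 0.25r)/0.75.

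- Variance ratio: v = [0.25·r(1−r) + 0.75·q(1−q)] / 0.21
- Unadjusted standard error: s = √(0.42/222) = 0.0435, so 0.11/s = 2.529
- Unadjusted power: Φ((2.529 − 1.960)/√v). The true spread is s√v although the test uses s.
- Adjusted power: Φ(2.529/√v − 1.960)
- True one-sided error of the unadjusted test: 1 − Φ(1.960/√v). This is an approximation that uses the 30% risk throughout.

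| r | q | v | Unadjusted power | Adjusted power | Gain (points) | True error, unadjusted |
|---|---|---|---|---|---|---|
| 0.30 (not prognostic) | 0.300 | 1.000 | 71.5% | 71.5% | 0 | 2.5% |
| 0.40 | 0.267 | 0.984 | 71.7% | 72.2% | 0.5 | 2.4% |
| 0.50 | 0.233 | 0.937 | 72.2% | 74.3% | 2.1 | 2.1% |
| 0.60 | 0.200 | 0.857 | 73.1% | 78.0% | 4.9 | 1.7% |

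The unadjusted baseline rises with r because stratified randomisation already lowers the true spread. Measuring the gain from a fixed 71.5% would overstate it.

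**Simulation check.** Assumed odds ratios for age and prior admissions, with assumed between-site spread; ICS figures assume no azithromycin effect.

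- Odds ratios 1.3 and 2: ICS power 72.0% to 72.9%, azithromycin 70.0% to 71.1%.
- Odds ratios 1.5 and 3: ICS 72.1% to 74.5%, azithromycin 69.5% to 72.2%.
- Odds ratios 1.5 and 5: ICS 72.9% to 78.5%, azithromycin 70.2% to 75.5%. The unadjusted one-sided error of the azithromycin test was about 1.7%.
- Strata not prognostic: no gain.

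**Could adjustment restore 80% power?** At 222 per side the covariates would have to explain 1 − [0.11/2.802]² / (0.42/222) = 18.5% of the variance for ICS, and 1 − [0.10/2.802]² / (0.37/222) = 23.6% for azithromycin. Even r = 0.60 above gives only 14.3% (1 − 0.857).

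**The case against.** The strongest reply is that the conflict is one of wording. The choice of covariates is commonly left to a statistical analysis plan, and a Cochran-Mantel-Haenszel test is itself a stratified chi-squared test, so such a plan could honour both sections. It is true that a chi-squared method could carry the adjustment. But the protocol does not name that version: it fixes a method in 5.1 that, read plainly, contradicts its own section 5. That is more than missing detail.

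Other parts of the reply stand and limit the point:

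- A reader might infer that omitting the other intervention costs power. It costs almost none; nearly all the possible gain comes from the strata, and that gain rests on assumed risks.
- A reader might infer a risk of false positive claims. The error runs the other way: the unadjusted test is conservative when the strata are prognostic.
- A reader might take the opening of 5.3 as making the four-arm comparison the main one. The protocol never gives it that status, and section 5 sizes two marginal comparisons. The sentence needs only clarifying.
- Section 5 says of the analysis teams: "These two analysis teams (separate) will be blinded to an effect estimate of the other intervention". A reader might infer that a regression term for the other factor must breach this, or that a masked code settles it. Neither follows. The protocol states the principle without a mechanism, and a team that holds outcomes and a masked code could still tabulate the size of the other effect, under a stratified method as much as under regression.
- Section 5.1 specifies no interval, so no stated interval is too wide. The loss concerns the unadjusted risk difference that the ICS non-inferiority question needs.

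**Conclusion.** The point holds in a limited form. Sections 5 and 5.1 contradict each other on whether the main analysis is adjusted, and the test named in 5.1 makes no use of the randomisation strata. If a quarter of participants are in the higher prior-admission group at 40–60% risk, using the strata is worth about 0.5 to 5 points of ICS power (about 2 at 50% risk). If the strata are not prognostic it is worth nothing. The prevalence and risks are assumptions, so the direction of the loss is firmer than its size. A reader might hope that adjustment would rescue the trial's power; the figures do not support this, and the sample-size shortfall is a separate matter. The change should be made because it removes a contradiction and may recover some precision at little cost.

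**What to change.** In 5.1, replace the plain chi-squared test with one primary analysis per intervention at the factorial margin (222 vs 222): a risk difference with confidence interval, either Mantel-Haenszel stratified or standardised from a logistic regression. Include the other randomised intervention, age group, prior-exacerbation group and site. State in 5.3 that comparisons among the four arms are descriptive or secondary.

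The cost is protocol wording and a slightly longer program. There is one small downside. With the six departments named in section 8, full cross-classification gives 6 × 2 × 2 × 2 = 48 cells of about 444/48 ≈ 9 participants, so a rule for pooling or modelling sparse site strata must be fixed in advance.
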